# **STUDY PROTOCOL**

## **1. BACKGROUND AND RATIONALE**

### **1.1. General Introduction**

The Chest Pain Choice (CPC) decision aid is a visual aid that was developed to facilitate shared decision-making between physicians and patients who present to the emergency department with chest pain. Shared decision making with the use of this visual aid has been shown in other centres to be associated with greater patient knowledge, greater patient involvement in decision making and less frequent admissions, with no increase in major adverse cardiac events (MACE) due to the intervention. The visual aid includes a brief description of what tests have been done thus far to assess the patient's risk of MACE, a graphic representation of the risk as calculated based on the HEART score, as well as the evaluation options available. The visual aid has been modified from its original form for the local context in terms of viable options for further evaluation. Please see Appendix 1 for an example of the CPC visual aid.

### **1.2. Rationale and justification for the Study**

This study aims to evaluate the use of the CPC decision aid as a tool to facilitate discussion between the patient and his/her attending physician with regard to subsequent management plans. Patients aged 21 years and above with low-risk chest pain, as determined by the HEART score (HEART score 0-3), will be included. Our hypothesis is that incorporating the Chest Pain Choice visual aid in shared decision making can help to reduce unnecessary admissions for low risk chest pain to the observation ward, as well as increase patient knowledge with regards to their own condition.

#### **a. Rationale for the Study Purpose**

Chest pain is a common presenting complaint in the Emergency Department (ED). Cardiac testing in low-risk patients poses unnecessary costs and resource utilisation, which may in part be due to clinicians adopting a very-low-risk threshold for discharge without testing. The use of the Chest Pain Choice - a visual aid - for shared decision making, has been shown to be effective in increasing patient knowledge and decreasing the rate of admission to an observation unit for cardiac testing, among patients with chest pain who are at low risk for acute coronary syndromes. This can be adapted to our local context to decrease unnecessary admissions to the ED observation unit (referred to as the Extended Diagnostic Treatment Unit or EDTU in our institution). This study aims to assess if using a visual decision aid for shared decision making between physician and patient can safely help to decrease unnecessary admissions to the ED observation unit, as well as its impact on patient knowledge, satisfaction, as well as 30-day and 60-day Major Adverse Cardiac Events (MACE).

#### **b. Rationale for Study Population**

The target population is that of adults aged 21 years and above who present to ED with chest pain that is considered low risk based on the HEART score (HEART score 0-3). The HEART score is a validated scoring system for patients aged 21 years and above who present with

symptoms suggestive of Acute Coronary Syndromes. The HEART score assigns different points for various features in the patient's history, ECG features, age group, presence of risk factors, and initial troponin level, in order to generate a score that corresponds to a range of percentages for the risk of 6-week MACE. Patients with a HEART score of 0-3 correspond to a 6-week MACE risk of 0.9-1.7%. Since the risk of 6-week MACE is low in these patients, outpatient follow-up and cardiac testing for underlying coronary artery disease can be considered instead of ED observation unit admission. This is also in keeping with current institutional practices.

### **c. Rationale for Study Design**

This is a randomized controlled trial where subjects will be stratified by gender and then randomized 1:1 to either the control or the intervention arm. This is because gender may affect the cardiovascular risk significantly and hence affect the outcome of MACE.

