**3.2. Criteria for Recruitment**

The patients will first be assessed by their primary physicians to ascertain if their chest pain is low-risk (based on the HEART score) and if they are suitable for recruitment. An initial serum troponin and ECG will be done prior to recruitment to risk stratify patients, and the consent process will take place only after the results of the serum troponin and ECG are released. Recruitment will take place from Sunday 0800 hours to Thursday 2359 hours, as inpatient stress testing or computed tomography of the coronary arteries in the ED observation unit are only available during weekdays.

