## **9. SAMPLE SIZE AND STATISTICAL METHODS**

### **9.1. Determination of Sample Size**

A sample size of 164 patients (82 in each arm) will provide 80% power to detect an absolute difference of 20% reduction in admissions to ED observation unit in the intervention arm between the 2 groups, with 2-sided alpha of 0.05.

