### **9.2. Statistical and Analytical Plans**

Intention-to-treat analysis will be carried out; proportions will be evaluated using chi-square tests, non-parametric variables with Mann-Whitney *U* and parametric variables with Student's *t* tests as appropriate.

An interim analysis will be done when 50% of recruitment has been reached to check for incidence of adverse outcomes such as 30-day or 60-day MACE. If there is a significant increase in 30-day or 60-day MACE in the intervention arm as compared to the control arm, the study will be stopped.

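### Section 9.2 leaves gender and the HEART score out of the primary admission comparison: a cheap gain in precision forgone, not a bias

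*Combined protocol and SAP*

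**What the plan says.** The primary objective (section 2.2) is a reduction in admissions to the ED observation unit at the index visit. Section 9.2 contains the whole analysis plan: intention to treat, with "proportions will be evaluated using chi-square tests" and Mann-Whitney or t tests for other variables. It names no covariate or stratified analysis for any outcome.

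Gender is the only baseline factor in the design. The rationale for study design (section 1.2) explains the stratification: "This is because gender may affect the cardiovascular risk significantly and hence affect the outcome of MACE". Section 5.1 gives the same reason.

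A HEART score of 0-3 is an inclusion criterion (section 3.3). Troponin and ECG results come before consent (sections 3.2 and 6.2), and envelopes are opened after recruitment (section 6.1). The score can therefore be fixed for every subject before allocation. Section 1.1 says that the aid includes "a graphic representation of the risk as calculated based on the HEART score".

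Section 9.1 states that 164 patients, 82 per arm, "will provide 80% power to detect an absolute difference of 20% reduction in admissions to ED observation unit in the intervention arm", "with 2-sided alpha of 0.05". It gives no control-arm admission rate. Section 3.1 plans 200 subjects, and section 3.6 makes 164 the minimum.

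**The concern.** Two baseline variables are available at no extra cost and neither enters the primary comparison. A factor used to stratify randomisation is normally carried into the analysis; if it predicts the outcome, leaving it out makes the test slightly conservative. Gender was also chosen with MACE in mind. At the protocol's own 0.9-1.7% risk, MACE would number about 164 x 0.009 = 1.5 to 200 x 0.017 = 3.4 in the whole trial. Nothing was chosen with admission in mind.

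The HEART score is the obvious candidate. Section 1.2 uses HEART-based risk to justify outpatient care in place of observation, and says that testing may partly reflect clinicians' very low risk threshold for discharge. If admission rises with the score even within 0-3, adjustment would tighten the estimate without recruiting anyone.

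Prespecification matters too. The trial is open-label, and an adjustment added after an imbalance had been seen would carry little weight.

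**Working it through.** **1. The plan's own figure.** Inputs from section 9.1: two-sided alpha 0.05, power 80%, absolute difference 0.20. The control rate is not given; 40% v 20% is an assumption, found by solving backwards.

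n per arm = [1.96 x sqrt(2 x 0.30 x 0.70) + 0.8416 x sqrt(0.40 x 0.60 + 0.20 x 0.80)]^2 / 0.20^2 = (1.270 + 0.532)^2 / 0.04 = 81.2, so 82.

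This matches the stated 164 in total, with power 0.804. No covariate is used, in line with section 9.2. At 100 per arm the same formula gives 0.876. At 60% v 40%, 82 per arm gives only 0.730.

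**2. Chance imbalance and its consequence.** Assume scores 0/1/2/3 in 10/25/35/30% of subjects. The between-arm difference in the share scoring 2-3 has SD sqrt(0.65 x 0.35 x 4/164) = 0.0745, so a gap of 10 points or more occurs in about 18% of trials. With 200 subjects the SD is sqrt(0.65 x 0.35 x 4/200) = 0.0675, and the figure is about 14%.

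The effect on the admission difference is the gap multiplied by the difference in admission between high and low scores:

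- Moderate gradient (control admission 20/30/41/54% by score): scores 0-1 average (10 x 20 + 25 x 30)/35 = 27%; scores 2-3 average (35 x 41 + 30 x 54)/65 = 47%. Shift: 0.10 x 20 = about 2 points.
- Steep gradient (9/20/41/65%): averages 17% and 52%. Shift: 0.10 x 35 = about 3.5 points.

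Both are small against the 20-point target.

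**3. Power with and without adjustment.** Trials were simulated at 82 per arm. The unadjusted chi-square was compared with a standardised risk difference from a logistic working model, with an influence-function standard error.

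With the score distribution and gradients of step 2 (6,000 trials per scenario):

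| Gradient | Rates | Unadjusted | Adjusted |
|---|---|---|---|
| Moderate | 40% v 20% | 80.5% | 82.5% |
| Steep | 40% v 20% | 80.1% | 85.5% |
| Moderate | 50% v 30% | 74.2% | 77.5% |

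A repeat run at 40% v 20% gave 79% to 81% (moderate), 81% to 87% (steep) and no change with no gradient.

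With scores at 10/20/30/40% and an assumed odds ratio per HEART point (3,000 trials per scenario, Monte Carlo error about 0.7 points):

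| Odds ratio per point | 40% v 20%: unadjusted, adjusted | 70% v 50%: unadjusted, adjusted |
|---|---|---|
| 1.0 | 0.798, 0.801 | 0.738, 0.747 |
| 1.25 | 0.807, 0.809 | 0.746, 0.762 |
| 1.5 | 0.804, 0.817 | 0.734, 0.759 |
| 2 | 0.804, 0.838 | 0.749, 0.803 |
| 3 | 0.799, 0.859 | 0.749, 0.854 |

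At 40% v 20% the variance ratio, unadjusted to adjusted, runs from 0.99 to 1.19. An odds ratio of 2 gives 1.08, worth about 0.08 x 164 = 13 patients.

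**4. Type I error.** With 50% admitted in both arms, the unadjusted test rejects in 4.6-5.1% of trials and the adjusted test in 4.9-5.0%. Under the step 2 assumptions, type I error was 5.0-5.4%.

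**5. At the planned enrolment.** With 100 per arm and 40% v 20%, power goes from about 88% unadjusted to about 88-91% adjusted, over gradients from none to steep.

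**The case against.** The strongest reply is that nothing here is wrong. An intention-to-treat chi-square test on a randomised comparison is valid, and its standard error already allows for chance imbalance. That stands. A reader might infer from the omission that the result would be biased by an uneven mix of scores; neither the design nor the simulated error rates support this.

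Second, the documents do not show that the score within 0-3 drives admission. A reader might infer that physicians use it to decide on discharge. Section 3.2 uses it to judge whether the pain is low-risk and the patient suitable for recruitment. Section 1.2 treats 0-3 as one group with one risk range. Where section 6 explains why usual care varies, it names social set-up and the availability of inpatient testing, not the score. The troponin and ECG criteria also limit variation in two of the score's five components. All of this stands, and it is why the range must include no gain.

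Third, the total score is not in section 6's list of data items, so it cannot be taken as recorded. Eligibility still requires it to be worked out, and the listed items (age, risk factors, symptoms, laboratory and ECG results) are its ingredients.

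Fourth, 82 per arm is the minimum. At 200 subjects, unadjusted power is already about 88% at 40% v 20%, so there is less to gain. That is true at those rates. The control rate is unstated, and power is lower nearer 50%.

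**Conclusion.** The point holds as a cheap improvement in precision and in prespecification. It is not a validity error. The relevant text is the test named in section 9.2. The gender sentence in section 1.2 is not itself wrong; it shows only that the stratification was chosen for MACE and not for admission.

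At 40% v 20%, the gain runs from nothing to about 6 points of power at 82 per arm (about 80% to about 80-87%), and from nothing to about 3 points at 200 subjects (about 88% to about 88-91%). It reaches about 10 points only at 70% v 50% with an assumed odds ratio of 3 per point. The control rate, the score distribution and the gradient are all assumptions; the documents give none of them. What does not depend on them is that type I error stays near 5% and that, with no gradient, essentially nothing is lost. The stated 164 need not change.

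**What to change.** In section 9.2, before any comparison of outcomes by arm:

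- Make the primary analysis of observation-unit admission a logistic model with arm, gender and HEART score (linear, 0-3). Report the standardised (marginal) risk difference with a robust 95% CI and test. This keeps the absolute difference on which section 9.1 is based.
- Keep the unadjusted chi-square test and the simple proportions as a supporting analysis.
- Make sure that the total HEART score, as established before allocation, is entered on the data collection form.

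The cost is a few lines of text and at most one field on the form, with no extra patients or assessments. The downsides are a model-based estimate beside the simple proportions, and a gain that may be near zero if the score within 0-3 does not predict admission.

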## **2. HYPOTHESIS AND OBJECTIVES**

### **2.1. Hypothesis**

Incorporating the Chest Pain Choice visual aid in shared decision making can help to decrease unnecessary admissions for patients with low risk chest pain to the observation ward, as well as increase patient knowledge with regards to their own condition.

### **2.2. Primary Objectives**

1. We aim to evaluate if shared decision-making with patients using the Chest Pain Choice (CPC), a visual decision aid tool, will reduce admissions to the ED observation unit among patients with low-risk chest pain at the index visit to the emergency department.

### **2.3. Secondary Objectives**

1. To determine if the CPC can improve patient knowledge and increase patient involvement in shared decision-making
2. To evaluate the impact on the incidence of MACE, ED re-attendances and downstream cardiac evaluation (either stress tests or computed tomography of the coronary arteries) at 30-days and 60-days with the implementation of CPC

### **2.4. Potential Risks and benefits:**

#### **a. End Points – Efficacy**

The direct benefits among research participants who are randomized to the CPC arm are that they may have a better understanding regarding their condition and feel more empowered in making a shared decision together with their attending physician.

The indirect benefit is that implementation of the CPC may safely reduce hospital admissions in patients with low-risk chest pain.

**b. End Points – Safety**

There is a potential risk of breach of confidentiality. However, all research data will be kept in a password protected personal computer and identifiers will be kept separately. Access to the data will only be kept within the study team, including the PI and the Co-investigators.

There is a potential risk that patients under the intervention arm may have a higher incidence of 30-day or 60-day MACE, as the hypothesis is that more patients will choose to be discharged rather than be admitted to the ED observation unit, which may lead to a delay in further cardiac testing and definitive management. However, this is unlikely as the study includes only patients with a low overall risk of MACE (0.9-1.7%) who are not likely to require any cardiac intervention.

**3. STUDY POPULATION**

**3.1. List the number of subjects to be enrolled.**

A total of 200 subjects will be enrolled at the National University Hospital Emergency Department. There are no restrictions based on race. The study excludes children as it is targeted at patients with low-risk chest pain in an adult emergency department.

**3.2. Criteria for Recruitment**

The patients will first be assessed by their primary physicians to ascertain if their chest pain is low-risk (based on the HEART score) and if they are suitable for recruitment. An initial serum troponin and ECG will be done prior to recruitment to risk stratify patients, and the consent process will take place only after the results of the serum troponin and ECG are released. Recruitment will take place from Sunday 0800 hours to Thursday 2359 hours, as inpatient stress testing or computed tomography of the coronary arteries in the ED observation unit are only available during weekdays.

**3.3. Inclusion Criteria**

The subject must meet all the inclusion criteria to participate in the study:

- Aged 21 years and above
- Have low risk chest pain as defined by the HEART score (0-3 points)
- Be English-literate
- Have an initial serum troponin that is less than the 99th centile of the normal reference population
- Have an initial electrocardiogram that is not suggestive of cardiac ischaemia

**3.4. Exclusion Criteria**

All subjects meeting any of the exclusion criteria at baseline will be excluded from participation:

- Have a HEART score of 4 or more

- Are not English-literate
- Have an elevated initial serum troponin
- Have an initial electrocardiogram that is suggestive of cardiac ischaemia (ST-segment depression or elevation, new onset left bundle branch block, T-wave inversions, etc.)
- Have known coronary artery disease
- Have a prior plan for cardiac intervention or admission
- Have barriers to outpatient follow-up
- Are prisoners
- Are pregnant
- Are hearing or visually impaired, or are otherwise unable to use the clinical decision aid
- Do not consent to participation in the study

### **3.5. Withdrawal Criteria**

The study may be continued if the intervention has been shown to be associated with an increase in 30- or 60-day MACE as compared to the control arm.

### **3.6. Subject Replacement**

Subjects who drop out will be replaced until the minimum number of 164 patients has been achieved.

## **4. TRIAL SCHEDULE**

Patients will be screened at the ED for suitability before consent is taken. The subject's direct involvement will only be during their ED visit. The subjects will then be followed up at 60 days for 30- and 60-day MACE via a review of their electronic medical records or via telephone contact if electronic medical records are not available. No other study visits are required.

	July 18	Aug 18	Oct 18	Nov 18	Dec 18	Jan 19	Feb 19	Mar 19	Apr 19	May 19	June 19	July 19	Aug 19	Oct 19	Nov 19	Dec 19
Application of DSRB	■															
Study Recruitment		■	■	■	■	■	■	■	■	■	■	■	■			
Follow-up of patients				■	■		■	■	■	■	■	■	■			
Analysis of data							■	■							■	■
Manuscript Writing																■
Publication of Data																■

## **5. STUDY DESIGN**

This is a randomized controlled trial where subjects are stratified by gender and then randomized 1:1 to the intervention (CPC) or control arm (usual care). The patient, attending physicians, and study team will not be blinded. Study recruitment will take approximately 12 months. Subjects are only directly involved during their ED visit, and will not be required to

participate in further follow-up sessions. Subjects will be followed up at 60 days by a review of their electronic medical records or via telephone only if no electronic records are available.

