The patients in both groups will be assessed regarding their pre- and post-consultation knowledge as well as satisfaction during this visit by standardized questionnaires. The patients will be followed up at 60 days to find out if they had MACE, ED re-attendances, as well as whether further tests for cardiac evaluation were done. This will be done via a review of their electronic medical records or via telephone contact if electronic medical records are not available. A MACE is defined as all-cause mortality, myocardial infarction or coronary revascularisation.

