### *c. Post Study Follow up and Procedures*

The subjects will then be followed up at 60 days for 30-day and 60-day MACE, repeat ED attendance, and subsequent cardiac testing performed via a review of electronic medical records or contact via telephone if electronic medical records are not available. No other study visits are required.

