## **8. DATA ANALYSIS**

### **8.1. Data Quality Assurance**

The principal investigator will review the study data on a quarterly basis for completeness. Data integrity will be assured by the means of doing spot checks on the data collected and comparison with the patient's electronic records.

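### Telephone follow-up is tied to records being unavailable, so almost nobody would be called and 60-day events outside the electronic record can be missed

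*Combined protocol and SAP*

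**What the plan says.** Four places set the follow-up rule, and all make record review the main route:

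- Section 4 (Trial Schedule): record review, or "via telephone contact if electronic medical records are not available".
- Section 5 (Study Design), the strictest: "via telephone only if no electronic records are available".
- Section 6 (Methods and Assessments): "The patients will be followed up at 60 days to find out if they had MACE, ED re-attendances" and further cardiac tests, with the same telephone fallback.
- Section 6.2.c: "contact via telephone if electronic medical records are not available".

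The safety outcome is broad: "A MACE is defined as all-cause mortality, myocardial infarction or coronary revascularisation" (section 6). MACE, re-attendance and downstream testing form the second secondary objective (section 2.3). MACE also decides whether the study stops (sections 7.3 and 9.2).

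Each subject has hospital data before enrolment, because the ECG and first troponin results must be in before consent (sections 3.2 and 6.2.a). Data quality is checked by "comparison with the patient's electronic records" (section 8.1).

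Three things are not stated: which hospitals or death records the electronic record covers, what counts as unavailable, and how a subject with no later entry is classified.

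**The concern.** The condition for a call is a property of the record, not of the follow-up information. A subject whose record holds the index visit and nothing afterwards does have a record, so the literal rule produces no call. Yet an empty record after discharge fits two situations equally well: nothing happened, or something happened where the record does not reach. All-cause death and care at another hospital are the obvious examples.

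Section 6.1 argues that bias is minimal because the outcomes are objective. Objectivity protects the classification of an event that is seen; it does nothing for one that is not. The team is also unblinded (sections 5 and 6.1), so an undefined trigger leaves the decision to call with people who know the allocation.

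At stake is the safety half of the question. Section 2.4.b itself names higher MACE in the intervention arm as a potential risk, and the expected count is so small that a single unseen event changes the picture.

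**Working it through.** **The plan's own figures.** The plan gives no figure for completeness of follow-up, so there is none to reproduce. The sample size of 164 (section 9.1) concerns index-visit admission and has no bearing here.

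**Inputs from the documents.** Enrolment: "A total of 200 subjects will be enrolled" (section 3.1), with a minimum of 164 (section 3.6). Risk: "Patients with a HEART score of 0-3 correspond to a 6-week MACE risk of 0.9-1.7" per cent (section 1.2.b). The six-week risk stands in for the 30- and 60-day risk.

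**Assumed input.** The share m of events outside the record is not in the documents; 10%, 20% and 30% are tried.

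**Step 1: does the trigger fire?** ECG and troponin results exist before consent, and data are checked against electronic records. That every subject therefore has a record is an inference, but a strong one. Under the section 5 wording, calls are then close to nil.

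**Step 2: expected MACE = N × risk.**

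- 200 × 0.009 = 1.8 and 200 × 0.017 = 3.4 in total, or 0.9 to 1.7 per arm.
- At the minimum of 164: 164 × 0.009 = 1.48 and 164 × 0.017 = 2.79.

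**Step 3: chance that at least one MACE is missed = 1 − (1 − risk × m)^N, with N = 200.**

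| m (assumed) | risk 0.9% | risk 1.7% | expected MACE still seen |
|---|---|---|---|
| 10% | 16.5% | 28.8% | 1.62 to 3.06 |
| 20% | 30.3% | 49.4% | 1.44 to 2.72 |
| 30% | 41.8% | 64.0% | 1.26 to 2.38 |

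**Step 4: chance of seeing no MACE at all = (1 − risk × (1 − m))^200.** With full capture it is 16.4% (risk 0.9%) or 3.2% (risk 1.7%). With m = 20% it is 23.6% or 6.5%.

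**Step 5: effect on the comparison.** If both arms capture the same share s, the observed risks are s × p1 and s × p0. The ratio p1/p0 is roughly preserved and the difference shrinks to s × (p1 − p0). Power to detect a doubling of MACE with 100 per arm is about 8% to 12% with full capture and about 7% to 10% with s = 0.8 (normal approximation, rough at such counts).

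**The case against.** **The wording may be meant more loosely.** Sections 4, 6 and 6.2.c could mean that no adequate record exists for the follow-up period; the literal reading leaves the telephone clause with almost nothing to do. That is a fair reading of intent, but it is nowhere written, and the word *only* in section 5 points against it.

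**The record may reach further than the recruiting hospital.** Nothing restricts it to one hospital. This stands: the loss could be small, and the documents cannot settle it. For the same reason, a reader should not infer that the plan codes silent records as event-free. It has no rule for them.

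**A reader might infer that the loss is worse in the CPC arm**, since the intervention aims at more discharges. The documents do not support a direction. Discharged patients may have outpatient tests or a Cardiology appointment (section 6), which would create later entries; tests may instead be done during the observation stay (section 6.2.b); and patients with barriers to outpatient follow-up are excluded (section 3.4). The direction could reverse.

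**A reader might also infer that about a third of events are lost.** That needs invented inputs. Suppose 80% to 90% of admitted and 60% of discharged patients return to the same system, with 40% v 20% admitted. Capture is then 0.4 × 0.8 + 0.6 × 0.6 = 68% (72% with 0.9) in control and 0.2 × 0.8 + 0.8 × 0.6 = 64% (66%) in CPC. None of these rates is documented as a return or admission rate. Even so, the gap of 4 to 6 points applied to 0.9 to 1.7 events per arm is only 0.04 to 0.10 of an event.

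**MACE power is negligible anyway.** True (step 5), so better capture will not make the comparison informative. It does make the reported counts, and the stopping decision that rests on them, trustworthy. Re-attendances and tests face the same gap, but the documents give no rates from which to size it.

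**Conclusion.** The concern holds. Taken literally, the rule triggers almost no calls, and no other section closes the gap. Events beyond the record's reach can be missed in both arms. The primary endpoint, admission at the index visit, is untouched; MACE, re-attendance, downstream testing and the MACE stopping rule are exposed.

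The size is conditional. At the protocol's own risk and 200 subjects, an assumed 10% to 30% of events outside the record gives a 16.5% to 64% chance of missing at least one of an expected 1.8 to 3.4 MACE. If the record covers all hospitals and deaths, the chance is far smaller. Differential loss by arm remains possible but unproven. This should be corrected because it is cheap to do, not because it undermines the main result.

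**What to change.** In sections 4, 5, 6 and 6.2.c, replace the trigger with record review plus one short scripted telephone call to every subject after day 60, in both arms, whatever the record shows. The script should ask about death, infarction, revascularisation, ED visits and cardiac tests at any hospital. Confirm reported events against source records, record the source of each outcome, and report subjects who are not reached and have a silent record as unknown, not as event-free.

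Calling only subjects without an encounter on or after day 60 would save calls, but an unrelated later visit would then suppress the call, and ascertainment would again depend on in-house contact.

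Alternatively, if the record can be shown to cover all hospitals and deaths, a statement to that effect in these sections would suffice.

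The cost is up to 200 short calls by the existing team, about 200 / 52 = 3.8 a week over the 12-month recruitment, by a route already in the protocol. The downside is some self-reported events to confirm.
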